1.0 Introduction and Background

It is estimated that one-third of the more than 7 million deaths from cancer worldwide is attributable to potentially modifiable risk factors, with 374,000 deaths preventable through diet modification alone (not including those attributable to obesity or physical inactivity).¹ Diet supplementation for the prevention of cancer is an attractive mechanism to control cancer, since it is easy to implement to a broad population, even populations with reduced incomes and resources. Grape extracts or active components isolated from grapes have received attention as chemopreventive agents based upon their anti-proliferative, anti-inflammatory and anti-oxidant properties.²

The muscadine grape (*Vitis rotundifolia*), found in the warm, humid climate of southeast United States, has a distinct phytochemical composition as compared to other grape varieties. The muscadine grape contains a high concentration of anthocyanin 3,5-diglucosides, ellagic acid, ellagic acid precursors, gallic acid, flavan-3-ols and flavonols.³ Several preclinical studies with muscadine grape products have revealed anti-tumor activity, including inhibition of tumor cell growth and induction of apoptosis.⁴⁻⁷ Evidence from preclinical trials also suggests that muscadine grape products may decrease systemic inflammation.⁸⁻¹¹ Higher levels of inflammation may not only increase cancer recurrence risk,¹² but also impair quality of life. Higher levels of systemic inflammation are associated with increased fatigue¹³, reduced levels of physical activity, adiposity^{14,15} and lower levels of physical function¹⁶⁻¹⁸. By reducing levels of circulating inflammatory markers such as CRP and IL-6, muscadine grape products may improve cancer outcomes by decreasing symptom burden (particularly fatigue).

Despite reports indicating potential anti-tumor activity,⁴⁻⁶ there are limited clinical studies on the efficacy of muscadine grape products in the prevention or treatment of cancer, representing an opportunity for novel investigations. The current study proposes to build upon promising preclinical and clinical studies to assess the safety and tolerability of a proprietary muscadine grape extract (MGE) formulation, made from muscadine grape skins and seeds and produced by Nature's Pearl, in a Phase 1 clinical trial of patients with metastatic solid tumors who have failed prior standard therapies.

1.1 **Preclinical Studies**

Literature overview: The anti-tumor properties of muscadine grapes have been demonstrated in preclinical models.⁴⁻⁷ Porter et al examined the effects muscadine grape extract on lung tumor formation in the fetus following transplacental exposure to a polycyclic hydrocarbon. Results indicated that muscadine exposure through drinking water reduces both tumor proliferation and angiogenesis, leading to a decrease in tumor burden and multiplicity in mouse models.¹⁹ Exposure to muscadine grape extract through drinking water similarly reduced breast tumor burden and multiplicity in c-neu mice.²⁰ In a study by God et al, four varieties of muscadine grape were tested and showed significant inhibition of 2-aminoanthracene mutagenesis, high antioxidant activity, and the ability to inhibit activities of metalloproteinases, implying that these muscadine products could be good inhibitors of carcinogenesis.⁶ In colon carcinoma cells, muscadine exposure induced cell death.^{4,5} In prostate cancer cell lines, treatment with muscadine grapes induced both cell cycle arrest and apoptosis.⁷ One mechanism by which muscadine grapes cause apoptosis is by downregulating the phosphatidylinositol 3-kinase (PI3K)/Akt survival pathway.⁷ The PI3K/Akt pathway is a key oncogenic signaling pathway that has been linked to tumorigenesis and resistance to anticancer therapies in a wide variety of tumor types.²¹ A study by Burton et al examined the effects of muscadine grape product on bone turnover in prostate and breast cancer cell models overexpressing Snail transcription

factor.²² They show that Snail regulation can be antagonized by muscadine exposure, leading to decreased cell invasion, migration and bone turnover, and thus suggesting that muscadine grapes could be a promising bioactive treatment for bone metastatic cancer.

Overview of preliminary data from the investigative team: Preliminary studies from the investigative team ([name]/[name]) demonstrate that muscadine grape seeds and skins reduced the proliferation of both human breast and prostate cancer cell lines. The reduction in breast cancer cell growth was associated with a decrease in activated mitogen activated protein (MAP) kinase, a critical enzyme involved in cell proliferation. In addition, muscadine grape liquid extract reduced the tumor burden in a transgenic model of spontaneous breast cancer with a concomitant attenuation in proliferation, tumor blood

vessel formation, and tumor-associated fibrosis. These data are described below and provide additional rationale to assess the efficacy of Nature's Pearl proprietary muscadine grape extract (MGE) on cancer outcomes in clinical studies.

Inhibition of Prostate Cancer Cell Proliferation by Muscadine Grape Components

Actively growing human LnCaP or PC3 prostate cancer cells were plated into individual wells of 24 well plates and treated for 7 days with increasing concentrations of extracts from either muscadine grape seeds or skins, to determine whether the extracts reduced prostate cancer cell proliferation. As shown in **Figure 1**, extracts from both grape seeds and skin reduced the proliferation of LnCaP or PC3 human prostate cancer cells. The responses were dependent upon the dose of extract that was used and similar responses were obtained with grape seed extract compared to grape skin extract.

Inhibition of Breast Cancer Cell Proliferation by Muscadine Grape Components

Actively growing human breast cancer cells— ZR-75-1 ER+ breast cancer cells, MDA-MB-231 or SKBR3 triple negative breast cancer cells--were plated into individual wells of 24 well plates and treated for 7 days with increasing concentrations of extracts from either muscadine grape seeds or skins, to determine whether the extracts reduced

Figure 1. LnCaP or PC3 human prostate cancer cells were incubated with increasing concentrations of either muscadine grape seed or grape skin extracts and cell proliferation was quantified by counting the number of cells per well. The data are presented as the percent of the Control (Con), which was not treated with either extract. n = 12, ** denotes p < 0.01.

breast cancer cell proliferation. As shown in **Figure 2**, extracts from both grape seeds and skin reduced the proliferation of ZR-75-1, MDA-MB-231 and SKBR3 human breast cancer cells. The responses were dependent upon the dose of extract that was used and similar responses were obtained with grape seed extract compared to grape skin extract.

Figure 2. ZR-75-1, MDA-MD-23 or SKBR3 human breast cancer cells were incubated with increasing concentrations of either muscadine grape seed or grape skin extracts and cell proliferation was quantified by counting the number of cells per well. The data is presented as the percent of the Control (Con), which was not treated with either extract. n = 9 for ZR-75-1 cells, 6 for MDA-MB-231 cells and 18 for SKBR3 cells; * denotes p < 0.05, ** denotes p < 0.01.

Inhibition of MAP Kinase Activity by Muscadine Grape Components

Human MDA-MB-231 or ZR-75-1 breast cancer cells were incubated with 50 µg/mL muscadine grape seed or grape skin extract for increasing periods of time. MAP kinase activity was quantified in cell extracts by Western blot hybridization using an antibody against phospho-ERK1/ERK2 from Cell Signaling. The decrease in phospho-ERK activity was calculated by densitometry using β-actin as a loading control. As shown in Figure 3, the extracts from both muscadine grape seeds and grape skins caused a significant reduction in phospho-ERK, suggesting that the extracts significantly reduced proliferation. There was no significant difference in the response to grape seed versus grape skin extracts.

Because treatment with muscadine grape

seeds versus skins showed no significant difference in effect on cancer cell lines, the additional preclinical studies were performed with a muscadine grape liquid extract containing both seeds and skins.

Reduction in Tumor Growth by Muscadine Grape Liquid Extract in c-neu Mice

The effect of muscadine grape liquid extract (MGLE) was tested on female FVB-Tq(MMTV) NKAMul/J transgenic mice, in which the activated rat Erbb2 (c-neu) oncogene, under the direction of the mouse mammary tumor virus promoter expressed specifically in the mammary gland (c-neu mice), form mammary tumors (the equivalent of human breast cancer) by 6 - 8 months of age. Mice were treated with MGLE beginning at 3 weeks of age (at the time of weaning) and were sacrificed at $7\frac{1}{2}$ months of age. The dose of MGLE was approximately 1 mg of phenolics for a 25 gram mouse (and is equivalent to approximately 10 tablespoons or 148 mL of extract per day for a 70 kg man and an average concentration of 20,000 mg of phenolics/liter of MGLE). The muscadine grape liquid extract was added to the drinking water. Eighteen mice were treated for an average of

in their drinking water beginning at 3 weeks of age. Control mice drank regular water. The mice were euthanized after 220 days and their mammary tumors were removed and weighed. n = 8-10, ** indicates p < 0.01.

220 days (beginning treatment at 21 days of age, at the time of weaning). Ten (10) mice drank regular drinking water (control) and 8 mice drank water containing the MGLE. Although all of the mice developed tumors throughout their mammary tissue, there was a significant difference in the weight of the tumor mass, as shown in **Figure 4**.

Mammary tissue was fixed in 4% formalin, paraffin embedded and sectioned into 5 micron sections, for immunohistochemical analysis. Sections were incubated with an antibody to Ki67, as a measure of cell proliferation. As shown in **Figure 5**, tumors from mice that drank MGLE had a significant decrease in the number of proliferating cells. These results indicate that muscadine grape liquid extract reduces cell proliferation, in agreement with reduction in cell number and MAP kinase activation observed in cultured breast cancer cells.

Tumor sections from c-neu mice drinking regular water (control) or MGLE were incubated with an antibody to the

endothelial cell marker, CD34, and vessels were identified by a combination of morphology and positive CD34 immunoreactivity. As shown in **Figure 6**, tumors from mice drinking MGLE had fewer blood vessels than mice drinking regular water, suggesting that the grape extract inhibits angiogenesis.

Interstitial tumoral fibrosis was quantified in breast tumor tissue sections from c-neu mice and stained with picrosirius red, a nonspecific collagen stain. Collagen reaction product was markedly reduced by MGLE administration as compared to controls (**Figure 7**). Treatment with the MGLE reduced interstitial fibrosis by more than 50%, indicating that the extract reduces cancer-associated fibrosis in breast tumors.

1.2 Preclinical toxicity studies with MGE

The animal studies above were performed with muscadine grape liquid extract from Nature's Pearl (Advance, NC), which was added directly to the rodent drinking water. To study the effects of muscadine grape extract in humans, the muscadine grape liquid extract is dried, converted to powder form, and encapsulated. This proprietary product produced by Nature's Pearl is the muscadine grape extract (MGE) used in the preclinical toxicity studies below and in the phase 1 clinical study proposed. However, because rodents do not swallow capsules, the MGE powder is reconstituted and added to the drinking water for the toxicity studies described below.

The primary goal of the rodent toxicity tests on the Nature's Pearl MGE was to identify the range of doses that caused no life-threatening or adverse effects, thereby providing critical information for conduct of a Phase I clinical trial to assess toxicity in humans with cancer and establishing an estimated clinical margin of safety. Toxicity tests on the proprietary MGE that will be used in clinical testing were performed in mice, to assess effects of the extract on the general health of the mice as well as their hearts, liver, lungs and kidneys.

Male C57 black mice (8 weeks of age) were randomized into groups to receive drinking water alone (control) or MGE in the drinking water at four escalating doses of MGE as determined by the measurement of total phenolics. Daily observations of the mice included evaluations for weight loss, diarrhea, dehydration, edema, abdominal enlargement or ascites, progressive dermatitis, rough hair coat or unkempt appearance due to lack of grooming, hunched posture indicative of pain, lethargy or persistent decumbency due to loss of appetite, coughing, labored breathing, nasal discharge, jaundice, cyanosis, pallor/anemia, neurological signs indicated by inappropriate head carriage or shaking of the head, bleeding from any orifice, or any condition interfering with daily activities. Prior to sacrifice, the mice were placed in metabolic cages for 24 hours, and food intake and fecal and urine output were measured to quantify markers of renal damage. During the 4th week of treatment, blood pressure was determined by tail cuff plethysmography in conscious mice and cardiac function was assessed in mice anesthetized with isofluorane, using the non-invasive, small animal VEVO ultrasound imaging system in the M and B modes, to measure or calculated election fraction, fractional shortening, stroke volume. heart rate and cardiac output were determined. The mice were sacrificed after one month of treatment; tissues (heart, kidney, lung, liver, spleen and brain) were weighed, fixed in 4% formalin, embedded in paraffin, sectioned at 5 microns and stained with Hematoxylin & Eosin (H & E) for analysis by a veterinary pathologist to assess any gross structural abnormalities.

Four concentrations of the MGE were tested. The range of concentrations to be tested was based upon previous studies in the [name]/[name] laboratory reported above. In those studies, a daily concentration of 1 mg of total phenolics/mouse/day was effective at reducing tumor multiplicity. For the toxicity studies in mice, the four doses of the MGE tested were 0.25, 0.5, 1.0 and 2.0 mg total phenolics/mouse/day, administered to the mice in their drinking water. Total phenolic content was determined using the Folin-Ciocalteau reagent with gallic acid as the standard. Since an average mouse of this age weighs approximately 25 g or 0.025 kg, this corresponds to a dose range of 10, 20, 40 and 80 mg total phenolics/kg/day. Based upon an average mass of 70 kg for a patient, this would correspond to 700, 1400, 2800, and 5600 mg phenolics/day. The proprietary Nature's Pearl muscadine grape extract capsule contains approximately 162 mg total phenolics/capsule, this would correspond to taking 5, 10, 21 and 42 capsules/day.

Results

During the 4 week administration of the MGE at the four doses, there were no observations of diarrhea, dehydration, edema, abdominal enlargement, loss of hair coat, reduced grooming, or decreased level of activity, appetite, drinking or breathing. There were no indications of pallor, jaundice or cyanosis or any neurological signs of discomfort. There was no bleeding or discharge. These results suggest that the mice were free from any pathology that affected their normal daily activities or health.

The mice were weighed at the end of the treatment period, to determine the effect of the MGE on total body weight. The weight of the mice at the end of the 4-week treatment period was similar with the three lowest concentrations of the MGE compared to the control group. Mice treated with the highest concentration of MGE had a small but significant decrease in total body weight (from 28.6 ± 1.2 grams to 25.0 ± 1.3 grams, which represents less than 15% of their total body weight). However, there was no effect on food intake, fecal output or urine volume compared to the untreated mice, measured during the last week of treatment, suggesting little effect of the MGE on eating and drinking behaviors.

At the time of sacrifice, various organs (heart, lung, liver, kidney, spleen and brain) were removed and weighed and the organ weights of mice treated with each dose of MGE were compared to the untreated control group. A portion of each organ was fixed in formalin, sectioned and stained with H & E. for assessment by a veterinary pathologist. In addition. the heart and kidney were assessed by echocardiography and radioimmunoassay of urinary proteins, respectively, as a further measure of heart and renal function. There was no difference in the weight or structure of the hearts of mice treated with increasing doses of MGE. Cardiac parameters including ejection fraction, fractional shortening, cardiac output, stroke volume and heart rate were all similar in mice treated with MGE compared to untreated Control mice. There was no difference in the weight or structure of the lungs of mice treated with MGE compared to the untreated control mice. The weight of the livers of mice treated with the two lowest MGE (0.25 and 0.5 mg phenolics/mouse/day) and the highest MGE (2.0 mg phenolics/mouse/day) concentrations were no different than the weight of the livers of the untreated mice. However, the weight of the livers of mice in the 1.0 mg phenolics/mouse/day) were slightly increased compared to the control. Spleen weight of mice treated with MGE was not significantly different than untreated control mice and the spleens of mice were generally within normal limits with one mouse in the highest MGE treatment group having some extra medullary hematopoiesis. The weight of the brains of mice treated with MGE was not significantly different than untreated mice. The brains were subdivided into four regions—cortex, cerebellum, hypothalamus and brainstem. All brain regions examined were within normal limits.

Conclusions from toxicity studies and corresponding clinical doses:

Little toxicity was observed at any of the doses tested. Therefore, the level of phenolics used to treat the mice suggests that this level of phenolics and corresponding numbers of capsules will likely be tolerated by patients. However, based upon patient compliance, a recommended dose range for patients would include 2, 4, 6, 8 and 10 capsules/day (corresponding to approximately 5, 9, 14, 18 and 23 mg phenolics/kg/day).

1.3 Clinical Studies

Muscadine grape skin extract has been evaluated in clinical trials to a limited extent in the setting of cardiovascular disease²³ and diabetes.²⁴ In a randomized, double-blind, placebo-controlled crossover trial, 50 adults with coronary disease or \geq 1 cardiac risk factor received muscadine grape seed supplementation (1300 mg daily) and placebo for 4 weeks each, with a 4-week washout, and no adverse events were reported.²³ Similarly, a randomized study of non-diabetic and type 2 diabetic participants using 150 mL of muscadine grape juice, muscadine grape wine, and dealcoholized muscadine grape wine over a 28-day period had no adverse events reported.²⁴

A muscadine grape product has also been examined in a phase 1/2 trial of men with biochemically recurrent prostate cancer.²⁵ The phase 1 portion of the study evaluated increasing doses of pulverized muscadine grape skin in a product called MPX (Muscadine Naturals Inc, Clemmons NC) in cohorts of two patients, with six patients at the highest dose of 4,000 mg (n=14). Dose selection was based on unpublished preclinical work in animal studies. Four patients experienced adverse gastrointestinal symptoms possibly related to the study agent, including grade 1 flatulence, grade 1 soft stools, and grade 1 burping. No other related adverse events were reported and one patient reported improvement of chronic constipation. Six of the 14 patients came off study for disease progression (five metastatic, one rising PSA) after exposure for a median of 15 months.

One patient came off study for myasthenia gravis that was unrelated to treatment. Seven patients remained on the study. The lack of dose-limiting toxicities led to the selection of 4,000 mg/d as the highest dose for further study. Median within-patient PSA doubling time increased by 5.3 months (non-significant, P=0.17). Based on the favorable safety profile and a possible lengthening of PSA doubling time, the phase 2 portion of this study was expanded to 125 patients randomized to placebo, 500 mg/d, or 4000 mg/d MPX arms. Recruitment was completed in October 2014 with results pending.

In summary, muscadine grape products have shown anti-cancer activity in preclinical models and have demonstrated a favorable safety profile in preclinical and clinical studies. This Phase 1 study using MGE represents an opportunity to translate promising preclinical data supporting the anti-cancer properties of a natural product into clinical trials.

2.0 Objectives

2.1 Primary Objective

2.1.1 To determine the safety and MTD of MGE after 4 weeks of administration for patients with metastatic solid tumors.

2.2 Secondary Objectives

- 2.2.1 To monitor adverse events/toxicity every 4 weeks while on treatment
- 2.2.2 To evaluate change in phenolic levels (total and component, blood and urine) from baseline to 4 and 8 weeks on MGE
- 2.2.3 To evaluate change in serum cytokines and growth factors from baseline to 4 and 8 weeks on MGE
- 2.2.4 To observe the response rate of MGE in patients with metastatic cancer.
- 2.2.5 To assess overall and progression-free survival in patients with metastatic cancer receiving MGE.
- 2.2.6 To assess global quality of life (FACT-G) and fatigue (PROMIS-fatigue short form) in cancer patients taking MGE.
- 2.2.7 To assess adherence to MGE treatment.

3.0 Patient Selection

3.1 Inclusion Criteria

3.1.1 Patients must have histologically confirmed solid tumor malignancy (excluding primary brain tumor) that is metastatic or unresectable and have failed standard therapies. Patients are also eligible if patients declined (or if their physicians determined them unsuitable for) standard therapy options.

$3.1.2 \ge 18$ years of age

- 3.1.3 The effects of MGE on the developing human fetus are unknown. Women of child-bearing potential and men must agree to use adequate contraception (hormonal or barrier method of birth control; abstinence) prior to study entry and for the duration of study participation. Should a woman become pregnant or suspect she is pregnant while participating in this study, she should inform her treating physician immediately.
- 3.1.4 Ability to understand and the willingness to sign an IRB-approved informed consent document.
- 3.1.5 ECOG performance status ≤ 2 .
- 3.1.6 Patients must have adequate organ and marrow function as defined below:
 - absolute neutrophil count >1000/mcL
 - platelets >50,000/mcL
 - total bilirubin
- within normal institutional limits
- AST(SGOT)/ALT(SGPT) <2.5 X institutional upper limit of normal
- creatinine clearance >40 mL/min
- 3.1.7 Stable supplement usage for >2 weeks prior to starting and agrees not to change while on this study.
- 3.1.8 Life expectancy \geq 3 months
- 3.1.9 Patients who declined standard therapies or whose physicians determined they were not suitable for standard therapy options are eligible.

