3.2 Exclusion Criteria

- 3.2.1 Patients who have had chemotherapy or radiotherapy within 2 weeks (6 weeks for nitrosoureas or mitomycin C) prior to entering the study or those who have not recovered from adverse events due to agents administered more than 2 weeks earlier.
- 3.2.2 Patients may not be receiving any other investigational cancer-directed agents.
- 3.2.3 History of allergic reactions attributed to compounds of similar chemical or biologic composition to MGE.
- 3.2.4 Patients unable to take oral medications or those with history of malabsorption due to bowel resection or gastrointestinal disease.
- 3.3.5 Patients with uncontrolled diarrhea or persistent nausea/vomiting requiring daily antiemetic therapy for symptom management within the past 21 days
- 3.2.6 Uncontrolled intercurrent illness including, but not limited to ongoing or active infection, symptomatic congestive heart failure, unstable angina

pectoris, cardiac arrhythmia, or psychiatric illness/social situations that would limit compliance with study requirements.

- 3.2.7 Pregnant women are excluded from this study because of potential for teratogenic or abortifacient effects with using MGE. Because there is an unknown but potential risk for adverse events in nursing infants secondary to treatment of the mother with MGE, breastfeeding should be discontinued.
- 3.2.8 Patients with primary brain tumors are excluded due to lack of data on MGE crossing the blood brain barrier. Patients with metastatic brain tumors may be enrolled.

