6.2 Treatment Administration

Treatment will be administered on an outpatient basis. Reported adverse events and potential risks are described in Section 8.0. No investigational or commercial agents or therapies other than those described below may be administered with the intent to treat the patient's malignancy.

Dose-Escalation Schedule				
Dose Level	Dose of MGE			
Level 1	1 pill po BID			
Level 2	2 pills po BID			
Level 3	3 pills po BID			
Level 4	4 pills po BID			
Level 5	5 pills po BID			

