6.4 General Concomitant Medication and Supportive Care Guidelines

Patients should receive *full supportive care*, including transfusions of blood and blood products, antibiotics, antiemetics, etc., as clinically indicated. Antiinflammatory or narcotic analgesics may be offered as needed. Medications considered necessary for the patient's well-being may be given at the discretion of the managing physician, i.e., chronic treatments for concomitant medical conditions, as well as agents required for life-threatening medical problems, etc. The reason(s) for treatment, dosage, and dates of treatment should be recorded on the flow sheets.

Participants on warfarin should have their INR checked within 2 weeks of starting MGE to ensure there is no clinically significant interaction. Further blood work to monitor warfarin levels are at the discretion of the treating physician per usual care.

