9.0 Pharmaceutical Information

Muscadine grape extract is a nutraceutical compound.

A list of the adverse events and potential risks associated with the investigational agent administered in this study can be found in Section 8.0.

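### Section 3.1.7 lets patients keep taking any stable supplement, including muscadine or grape-extract products, so phenolic intake can exceed the assigned dose level

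*Combined protocol and SAP*

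**What the plan says.** Section 3.1 (3.1.7) sets the only rule on supplements: "Stable supplement usage for >2 weeks prior to starting and agrees not to change while on this study". The rule is the same for every product.

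Three other places could have narrowed it:

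- Section 3.2 (3.2.2): "Patients may not be receiving any other investigational cancer-directed agents". A retail grape supplement is not an investigational agent. Item 3.2.3 excludes patients with past allergy to compounds resembling MGE, but not patients who currently take them.
- Section 6.2: "No investigational or commercial agents or therapies other than those described below may be administered with the intent to treat the patient's malignancy". This does reach commercial products, but only when they are taken against the cancer.
- Section 6.4: "Medications considered necessary for the patient's well-being may be given at the discretion of the managing physician". Supplements are not mentioned.

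Section 9.0 describes the study agent itself as a supplement-type product: "Muscadine grape extract is a nutraceutical compound". Section 1.3 describes other muscadine seed and skin products that have been given to people.

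The schedule in 6.1 collects concurrent medications pre-study, at weeks 4 and 8, and every 4 weeks after that. It does not name supplements, and no analysis in section 12 uses this record.

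**The concern.** The trial attributes toxicity to a dose level, and each level is judged on 3 to 6 patients. A patient already taking a muscadine or grape-seed capsule for general health meets 3.1.7, agrees to continue it, and is analysed at the assigned level. That patient's real intake of the compounds under study is higher than the level implies. If the excess raises the chance of a DLT, the event counts against a level that did not supply the whole exposure, and the design is more likely to stop early.

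Objective 2.2.2 is also touched: "To evaluate change in phenolic levels (total and component, blood and urine) from baseline to 4 and 8 weeks on MGE". A user's baseline sample already contains background phenolics of the same class. The working below separates what this affects from what it leaves intact.

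**Working it through.** **Inputs from the documents.** Section 1.2: "The proprietary Nature's Pearl muscadine grape extract capsule contains approximately 162 mg total phenolics/capsule", with the conversion to body weight "Based upon an average mass of 70 kg for a patient". Section 6.2: Levels 1 to 5 are 1 to 5 pills twice daily, that is 2, 4, 6, 8 and 10 a day.

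**Reproducing the plan's figures.** Phenolics per kg = capsules × 162 ÷ 70. This gives 4.63, 9.26, 13.89, 18.51 and 23.14 mg/kg/day. Section 1.2 states approximately 5, 9, 14, 18 and 23, so the figures agree to the precision claimed (18.51 is given as 18).

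**Assumption.** Own use is 1 or 2 capsule-equivalents a day at 162 mg each. The relative excess is extra capsules ÷ assigned capsules.

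| Level | Assigned mg/day | Excess with 1 extra | Excess with 2 extra | Total with 2 extra |
|---|---|---|---|---|
| 1 | 324 | 50% | 100% | 648 mg (9.3 mg/kg) |
| 2 | 648 | 25% | 50% | 972 mg (13.9 mg/kg) |
| 3 | 972 | 17% | 33% | 1296 mg (18.5 mg/kg) |
| 4 | 1296 | 12.5% | 25% | 1620 mg (23.1 mg/kg) |
| 5 | 1620 | 10% | 20% | 1944 mg (27.8 mg/kg) |

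Adjacent levels differ by 2 capsules (324 mg). Two equivalents therefore move a patient at Levels 1 to 4 exactly one level up, and a patient at Level 5 above the top planned level.

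**How likely is a user?** Prevalence is assumed. The chance of at least one user among n patients is 1 − (1 − q)^n.

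| Assumed q | Cohort of 3 | 30 patients (5 levels × 6) |
|---|---|---|
| 2% | 6% | 45% |
| 5% | 14% | 79% |
| 10% | 27% | 96% |
| 20% | 49% | >99% |

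**Effect on escalation.** In the 3+3 design, P(escalate) = P(0 DLTs in the first 3) + P(1 in the first 3) × P(0 in the next 3). Suppose one of the first three patients carries the next level's DLT risk and all others carry the current level's risk. For 10% against 20%:

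- No user: 0.9³ + 3(0.1)(0.9²) × 0.9³ = 0.729 + 0.243 × 0.729 = 0.906.
- One user: P(0) = 0.8 × 0.81 = 0.648. P(1) = 0.2 × 0.81 + 0.8 × 0.18 = 0.306. Then 0.648 + 0.306 × 0.729 = 0.871.

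| Assumed DLT risk, current vs next level | No user | One user in three | Fall in points |
|---|---|---|---|
| 5% vs 10% | 0.973 | 0.963 | 1.0 |
| 10% vs 20% | 0.906 | 0.871 | 3.5 |
| 20% vs 30% | 0.709 | 0.661 | 4.8 |
| 20% vs 40% | 0.709 | 0.613 | 9.6 |

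**Effect on the phenolic analysis.** Section 12.2.2 estimates change from baseline with subject as a random effect. If background B is constant and adds to the MGE contribution, the change is (B + MGE) − B = MGE, so the background cancels. It does not cancel in absolute on-study levels or in the spread between patients.

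**The case against.** The strongest reply is that the harm is conditional. The documents give no prevalence of use and no phenolic content for any product other than the study capsule, so every size above rests on assumption. Escalation shifts only if a user enrols and the extra intake changes DLT risk. Even the assumed 27.8 mg/kg/day at Level 5 lies within the 10 to 80 mg/kg/day tested in mice, where section 1.2 reports little toxicity. The bar in 6.2 on commercial agents with anticancer intent also closes part of the gap. All of this stands and limits the size of the point, but not its existence: use for general health remains open, and 3.1.7 asks for it to continue.

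Three stronger readings are tempting, and the documents do not support them:

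- A reader might infer that the phenolic baseline is wrong. It is a true measurement of the patient's background, and the stability that 3.1.7 requires is what protects the change-from-baseline contrast.
- A reader might infer that the extra intake goes unrecorded. Concurrent medications are collected, and the eligibility checklist and baseline form are separate attachments not available here. What can be said is that 6.1 does not name supplements and no planned analysis uses them.
- A reader might infer that users have already shown tolerance, which would select against DLTs. Nothing in the documents supports this, and it pulls in the opposite direction from the higher-intake argument.

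**Conclusion.** The gap in the eligibility text is real, and its consequence is conditional. Followed exactly, the plan lets a patient take study-agent-class phenolics on top of the assigned level. At 1 to 2 assumed capsule-equivalents a day the excess is largest at Level 1 and smallest at Level 5. One such patient among the first three lowers the probability of escalating by about 1 to 10 points under the assumed DLT risks, which pushes towards a lower MTD.

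It would be going too far to conclude that the dose or the MTD is wrong. The assigned MGE dose is correct in every case, and the MTD is affected only if users enrol and their extra intake alters DLT risk. Under constant, additive background, the planned phenolic change is unaffected; absolute on-study levels and between-patient spread are not protected. This is a cheap improvement to dose attribution, not a flaw that invalidates the design.

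**What to change.** Add to 3.2 an exclusion for concurrent use of muscadine, grape-seed or grape-skin extract supplements, with any abstinence period before the first dose set by the sponsor. Reword 3.1.7 so that it applies to all other supplements; otherwise a user who stops such a product would breach the agreement not to change. Keep the list to these named products, since a wider term such as concentrated polyphenols would need a definition the protocol does not have. Bring the eligibility checklist into line if it does not already cover this.

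The cost is one exclusion line and a small edit to 3.1.7. No procedure, dose level or sample size changes: the levels stay at 324 to 1620 mg/day and the maximum stays at 30. The downside is that users of these products, probably few, must stop them or are not enrolled.

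If the sponsor prefers to allow such products, the protocol should say so, record product and daily amount explicitly at baseline and each visit, and repeat the DLT-by-level and phenolic summaries without users. That keeps those patients, but in cohorts of 3 to 6 the repeat summaries will be sparse.
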